### 5.1.2 Justification for Study Design

The MET42 study is part of an ongoing development program that focuses on demonstrating that the safety profile of the MenACYW conjugate vaccine is similar to that of licensed MCV4, and that the immunogenicity of the MenACYW conjugate vaccine is non-inferior to licensed comparators in direct comparison trials. MET42 is a pivotal Phase III immunogenicity and safety study in which the vaccine candidate will be evaluated in infants/toddlers receiving concomitantly administered routine pediatric vaccines in the US. This study is designed to evaluate the safety and the immunogenicity of MenACYW conjugate vaccine following a 4-dose vaccination series in comparison to the licensed comparator MENVEO® in this population. Enrolment in the study will start at 6 to 8 weeks of age.

The concomitant administration of routine pediatric vaccines together with 5 different administration schedules of the MenACYW conjugate vaccine has been assessed in infants/toddlers 2 to 15 months of age in the US in study MET39. The subjects received either during or prior to the study, a number of licensed recommended vaccines at 2, 4, and 6 months of age: Pentacel®, either Prevnar® or Prevnar 13®, RotaTeq® or ROTARIX®, and ENGERIX-B® or RECOMBIVAX HB®. All subjects received M-M-R® II and VARIVAX® at 12 months. A total of 457 subjects completed the study. The immunogenicity and safety profiles of selected licensed pediatric vaccines (Pentacel®, Prevnar® or Prevnar 13®, M-M-R® II, and VARIVAX®) were assessed when administered either concomitantly with or without MenACYW conjugate vaccine. There was no evidence of interference with the pediatric routine vaccines administered concomitantly with MenACYW conjugate vaccine and the vaccine was safe and well tolerated regardless of the number of doses administered during the first year of life.

In the US, meningococcal vaccination is not routinely recommended for children aged  $\leq$  10 years; however, the vaccination is recommended for all individuals at increased risk of disease. ACIP recommends routine administration of MCV4 for all persons aged 11 through 18 years. A single dose of vaccine should be administered at age 11 or 12 years, and a booster dose should be administered at age 16 years. The ACIP also recommends meningococcal vaccination of individuals at increased risk of disease including infants. Since MENVEO® is the only MCV4 vaccine licensed for use in infants/toddlers in the US, the selection of MENVEO® as a comparator will contribute towards the total database of subjects that is compared to the competitor's product in the final dossier and will be beneficial for the Food and Drug Administration (FDA) review of the file.

Given that the meningococcal vaccines (investigational and control) used in this study have different appearances and preparation methods, and that vaccination schedule in the second year of life differs in the number of vaccines administered and timing of their administration, the study has a partially modified double blind design. The study is conducted as a modified double blind for the infant part of the study, with everyone involved in the study (participants/parents,

investigators, safety outcome assessor, Sponsor) blinded to the meningococcal vaccine received, except the personnel administering the vaccine. An unblinded vaccine administrator will administer the appropriate vaccine but will not be involved in safety data collection. The CRB will be design to ensure that the blind nature of the study will be maintained during the study. However, during the toddler part of the study, individuals blinded during the infant part of the study might be potentially unblinded due to the different timing of and age of the subjects at the vaccination visits and the number of vaccines received during these visits. Conducting the study in this manner will allow the blinded evaluation of safety data to the extent the study design permits.

### 5.1.3 Study Plan

#### *Vaccination*

A schedule of assessments and study vaccinations is provided in the Tables of Study Procedures and in [Table 5.1](#).

#### *Blood Sampling*

All subjects in the study will have 4 blood draws each. [Table 5.1](#) presents the schedule for blood-sampling. The schedule of antigen testing is detailed in [Table 5.2](#).

**Table 5.1: Vaccination and blood sampling schedule**

Group	Visit #	Age in months		4 months		6 months		7 months		12 months		13 months		15 months		16 months	
		Blood Draw ‡	Vaccines	Visit 1	Visit 2	Visit 3	Visit 4	Visit 5*	Subgroup	Blood Draw ‡	Vaccines	Blood Draw	Blood Draw ‡	Vaccines	Blood Draw ‡	Vaccines	Blood Draw
1	X	MenACYW Pentacel PCV13 rotavirus hepatitis B §	MenACYW Pentacel PCV13 rotavirus	MenACYW Pentacel PCV13 rotavirus hepatitis B			X	1a	X		MenACYW MMR varicella PCV13	X		No study visit Pentacel **			
								1b			MMR varicella PCV13	No study visit	X	MenACYW Pentacel hepatitis A	X		
2	X	MENVEO Pentacel PCV13 rotavirus hepatitis B §	MENVEO Pentacel PCV13 rotavirus	MENVEO Pentacel PCV13 rotavirus hepatitis B			X	2a	X		MENVEO MMR varicella PCV13	X		Pentacel hepatitis A			
								2b									

\*Visit 5 will occur at 12 months of age for Subgroups 2a and 2b, and at 12 to 15 months of age for Subgroups 1a and 1b.

†Last study visit for Subgroup 1a. Routine vaccines can be administered as per standard of care after study procedures are completed. Visit 6 will occur at 13 to 16 months of age for Subgroup 1a. For Subgroup 2a Visit 6 occurs at 13 months of age.

‡Blood will be drawn prior to vaccinations.

§The first dose of HB vaccine must have been received at least 28 days prior to the first study vaccination at Visit 1. Subjects in Subgroup 1a will complete the last study visit at 13 to 16 months of age. Pentacel will be provided by the Sponsor to complete the DTaP series with vaccine from the same manufacturer and should be administered as per standard of care. The study personnel / Investigator will be responsible for administering this dose at the recommended age outside of the scope of the study.

**Table 5.2: Schedule of antigen testing**

Visit #	Age in months	16 months*			15 months*			16 months*		
		Visit 1 (pre-vaccination)	Visit 4	Visit 5 (pre-vaccination)	Visit 6: 1a and 2a	Visit 6: 1b and 2b (pre-vaccination)	Visit 7: 1b and 2b			
Group	Subgroup									
Group 1 (N=1752)	Meningococcal serogroups A, C, W, Y Hib (PRP) Hep B (HBsAg) Poliovirus (types 1, 2, 3) Pertussis (PT, FHA, PRN, FIM) Rotavirus (IgA)	1a (N=1168)	Meningococcal serogroups A, C, W, Y Mumps Rubella Varicella PCV13†	Meningococcal serogroups A, C, W, Y Measles Mumps Rubella Varicella PCV13†	Pertussis (PT, FHA, PRN, FIM) Meningococcal serogroups (A, C, W, Y) Hib (PRP)	Pertussis (PT, FHA, PRN, FIM) Meningococcal serogroups (A, C, W, Y) Hib (PRP)	Pertussis (PT, FHA, PRN, FIM) Meningococcal serogroups (A, C, W, Y) Hib (PRP)			
		1b (N=584)								

Age in months		2 months	7 months	12 months*	13 months*	15 months*	16 months*
Visit #	Visit 1 (pre-vaccination)	Visit 4		Visit 5 (pre-vaccination)	Visit 6: 1a and 2a	Visit 6: 1b and 2b (pre-vaccination)	Visit 7: 1b and 2b
Group		Subgroup					
Group 2 (N=876)	Meningococcal serogroups A, C, W, Y Hib (PRP) Hep B (HBsAg) Poliovirus (types 1, 2, 3) Pertussis (PT, FHA, PRN, FIM) Rotavirus (IgA) PCV13† Rotavirus (IgA) Diphtheria Tetanus	2a (N=584)	Meningococcal serogroups A, C, W, Y Mumps Rubella Varicella PCV13†	Meningococcal serogroups A, C, W, Y Measles Mumps Rubella Varicella	Pertussis (PT, FHA, PRN, FIM) Hib (PRP) Polio (types 1,2, 3) Diphtheria Tetanus	Pertussis (PT, FHA, PRN, FIM) Hib (PRP)	Pertussis (PT, FHA, PRN, FIM) Hib (PRP)
Blood volume	3 mL	6 mL		5 mL	5 mL	5 mL	5 mL

Note: For each visit and group or subgroup, antigens are listed in descending order of assay priority (highest to lowest priority).

\*During the 2nd year of life, study visits, if blood is collected as part of the study, additional blood can be optionally collected via the same venipuncture for screening of iron deficient anemia and/or lead level as per AAP/CDC recommendations. This collection must be done in serum tubes not provided as part of the study and as per local standard of care.

†Anti-pneumococcal serotypes 1, 3, 5, 6A, 7F, 19A, 4, 6B, 9V, 14, 18C, 19F, and 23F.

### ***Collection of safety data***

- All subjects will be followed for safety from Visit 1 to 6 months after the last vaccination
- All subjects will be observed for 30 minutes after each vaccination, and any unsolicited systemic AEs occurring during that time will be recorded as immediate unsolicited systemic AEs in the CRB.
- The subject's parent / guardian will record information in a diary card about solicited reactions from D0 to D07 after each vaccination and unsolicited AEs from D0 after each vaccination to the next study visit.
- SAEs and MAAEs will be recorded throughout the study. The subject's parent/guardian will record information in a diary card about SAEs and MAAEs from V01 to V02, from V02 to V03, from V03 to V04, from V04 to V05, from V05 to V06, from V06 to V07 (for Subgroups 1b, 2a, and 2b), and from V07 to V08 (for Subgroup 2a only). SAEs and MAAEs will also be recorded in a memory aid (MA) from D31 after the last vaccination visit, until the 6-month follow up phone call. The subject's parent/guardian will be asked to notify the site immediately about any potential SAE at any time during the study.
- Staff will contact the subjects' parent/ guardian by telephone 8 days (+2 days) after each vaccination visit to identify the occurrence of any SAEs (including AESIs) and/or MAAEs not yet reported and to remind them to complete the diary card and to bring it back at the subsequent visit.
- The completed diary cards will each be collected and reviewed with the subject's parent/ guardian at the subsequent visit.
- Staff will contact the subjects' parent/ guardian by telephone within 14 days before V05 to remind them about the forthcoming study visit. If the subject's participation in the study is discontinued, the information recorded on the diary card will be reviewed at this time and the diary card will be retrieved by the site.
- Staff will contact the subjects' parent/ guardian by telephone at 6 months (+30 days) after the last vaccination visit to review the MA and identify the occurrence of any MAAEs and SAEs (including AESIs) that have not been reported.

#### **5.1.4 Visit Procedures**

The steps for Visit 1 through Visit 4 (during infancy) are presented for all subjects under [Section 5.1.4.1](#), since the procedures are common to all subjects. [Section 5.1.4.2](#) describes the visit procedures for the remaining visits; the visits are listed separately for each Subgroup since the number, timing, and details of each visit vary by Subgroup.

##### **5.1.4.1 Infant Vaccination**

###### **Visit 1 (D0; 2 months of age): Inclusion, Randomization, Blood Sample, and Vaccination**

- 1) Give the parent / guardian information about the study, obtain written informed consent, and give him/her a signed copy.
- 2) Check inclusion and exclusion criteria for eligibility.

- 3) Collect demographic data.
- 4) Obtain verbal medical history about the subject, including ongoing medications. Collect maternal immunization history (Tdap and meningococcal vaccinations) ([Section 5.2.6](#)).
- 5) Perform a physical examination, including, but not limited to, examination of the head (ear, nose, and throat), neck, heart, lungs, abdomen, and extremities. If a routine examination had been performed within the past week by a qualified health care provider, it does not need to be repeated unless there were changes in health status, in which case it may be limited to the affected area.
- 6) Measure temperature. If the temperature is  $\geq 38^{\circ}\text{C}$  ( $\geq 100.4^{\circ}\text{F}$ ), postpone vaccination until the condition is resolved.
- 7) Contact the interactive response technology (IRT) system for randomization, subject number, and vaccine allocation.
- 8) Review temporary contraindications for blood sampling. Ensure the subject has not had any antibiotics within the previous 72 hours (3 days).
- 9) Collect 3 mL of blood (BL1) (see [Section 7](#) for detailed instructions regarding the handling of blood samples). If the blood sample cannot be obtained, the parent/guardian should be given the opportunity to bring the subject back to the study site for another attempt, as long as the subject continues to remain eligible for the trial. All attempts should be made to obtain a blood sample; however, if the attempts are unsuccessful, the subject could continue in the study with all the study procedures including vaccination.

10) Review warnings and precautions to vaccinations.

11) Administer the following study vaccines. Each vaccine should be administered in the assigned location (see Operating Guidelines) and documented appropriately:

- Meningococcal vaccine (MenACYW conjugate vaccine or MENVEO®): inject IM into the anterolateral area of the thigh, preferably the right thigh.
- ENGERIX-B®: inject IM into the anterolateral area of the thigh, preferably the right thigh.
- Pentacel®: inject IM into the anterolateral area of the thigh, preferably the left thigh (i.e., the opposite leg from that used for meningococcal vaccine administration).
- Prevnar 13®: inject IM into the anterolateral area of the thigh, preferably the left thigh (i.e., the opposite leg from that used for meningococcal vaccine administration).
- RotaTeq®: administer orally per instructions in the package insert.

When multiple vaccines are administered at a single visit, each vaccine should be administered at a different anatomic site. If vaccines are given in the same limb, the injection sites should be separated by 1 inch or more, so that any local reactions can be differentiated ([39](#)).

Meningococcal vaccine and Engerix-B® should be given in the same thigh. Pentacel® or PREVNAR 13® should not be administered in the same thigh as the meningococcal vaccine. For details see Operating Guidelines.

Failure to administer vaccines in the designated limb will not constitute a protocol deviation, but should be recorded as a comment in the CRF. If the vaccines are not administered in the recommended limb(s), this should be corrected for subsequent injections.

- 12) Observe the subject for 30 minutes and record any AEs in the source document. In the event of a local reaction, indicate the associated vaccine.
- 13) Give the parent / guardian a diary card (DC1), a thermometer, and a ruler, and go over the instructions for their use. Instruct the parent / guardian to retain the thermometer and ruler throughout the duration of the study. At each subsequent visit, confirm that the parent /guardian has retained the thermometer and ruler, replace only as necessary.
- 14) Remind the parent / guardian to expect a telephone call 8 days after Visit 1 and to bring back the diary card when they return for Visit 2 at a specified date and time.
- 15) Remind the parent / guardian to notify the site in case of an SAE.
- 16) Complete the relevant case report forms (CRFs) for this visit.

#### **Telephone Call 1 (8 [+2] days after Visit 1)**

**Note:** If day 8 after vaccination falls on a weekend or a holiday, the telephone call may be made on the following business day.

- 1) Record relevant information concerning the subject's health status on the telephone contact form. If an SAE, including an AESI, has occurred, follow the instructions in [Section 10](#) for reporting it.
- 2) Remind the parent / guardian to do the following:
  - Complete the D0 to D07 pages of the diary card.
  - Complete the remaining pages of the diary card, and bring them to the next visit.
  - Notify the site in case of an SAE.

#### **Visit 2 (60 [+14] days after Visit 1; 4 months of age): Collection of Safety Information and Vaccination**

- 1) Collect and review the diary card (DC1) with the parent / guardian, including any AEs, medications, or therapy that occurred since vaccination. If an SAE, including an AESI, has occurred, follow the instructions in [Section 10](#) for reporting it.
- 2) Review warnings and precautions to vaccinations.
- 3) Review contraindications to subsequent vaccinations and conditions for withdrawal.
- 4) Measure temperature. If the temperature is  $\geq 38^{\circ}\text{C}$  ( $\geq 100.4^{\circ}\text{F}$ ), postpone vaccination until the condition is resolved.
- 5) Contact IRT system for vaccine assignments.
- 6) Administer the following study vaccines. Each vaccine should be administered in the assigned location and documented appropriately.

- Meningococcal vaccine (MenACYW conjugate vaccine or MENVEO®): inject IM into the anterolateral area of the thigh, preferably the right thigh.
- Pentacel®: inject IM into the anterolateral area of the thigh, preferably the left thigh (i.e., the opposite leg from that used for meningococcal vaccine administration).
- Prevnar 13®: inject IM into the anterolateral area of the thigh, preferably the left thigh (i.e., the opposite leg from that used for meningococcal vaccine administration).
- RotaTeq®: administer orally per instructions in the package insert.

When multiple vaccines are administered at a single visit, each vaccine should be administered at a different anatomic site. If vaccines are given in the same limb, the injection sites should be separated by 1 inch or more, so that any local reactions can be differentiated.

Pentacel® or PREVNAR 13® should not be administered in the same thigh as the meningococcal vaccine. For details see Operating Guidelines.

Failure to administer vaccines in the designated limb will not constitute a protocol deviation, but should be recorded as a comment in the CRF. If the vaccines are not administered in the recommended limb(s), this should be corrected for subsequent injections.

- 7) Observe the subject for 30 minutes and record any AEs in the source document. In the event of a local reaction, indicate the associated vaccine.
- 8) Give the parent / guardian a diary card (DC2).
- 9) Remind the parent / guardian to expect a telephone call 8 days after Visit 2 and to bring back the diary card when they return for Visit 3 at a specified date and time.
- 10) Remind the parent / guardian to notify the site in case of an SAE.
- 11) Complete the relevant CRFs for this visit.

### **Telephone Call 2 (8 [+2] days after Visit 2)**

Refer to steps in Telephone Call 1.

### **Visit 3 (60 [+14] days after Visit 2; 6 months of age ): Collection of Safety Information and Vaccination**

**Note:** Visit 3 has to occur when (1) age of subject is between 164 and 224 days; and (2) interval from Visit 2 is 60 [+14] days.

- 1) Collect and review the diary card (DC2) with the parent / guardian, including any AEs, medications, or therapy that occurred since vaccination. If an SAE, including an AESI, has occurred, follow the instructions in [Section 10](#) for reporting it.
- 2) Review warnings and precautions to vaccination.
- 3) Review contraindications to subsequent vaccinations and conditions for withdrawal.
- 4) Measure temperature. If the temperature is  $\geq 38^{\circ}\text{C}$  ( $\geq 100.4^{\circ}\text{F}$ ), postpone vaccination until the condition is resolved.

- 5) Contact IRT system to receive vaccine assignments.
- 6) Administer the appropriate study vaccines as described for Visit 1.
- 7) Observe the subject for 30 minutes and record any AEs in the source document. In the event of a local reaction, indicate the associated vaccine.
- 8) Give the parent / guardian a diary card (DC3).
- 9) Remind the parent / guardian to expect a telephone call 8 days after Visit 3 and to bring back the diary card when they return for Visit 4 at a specified date and time.
- 10) Remind the parent / guardian to notify the site in case of an SAE.
- 11) Complete the relevant CRFs for this visit.

#### **Telephone Call 3 (8 [+2] days after Visit 3)**

Refer to steps in Telephone Call 1.

#### **Visit 4 (30 [+21] days after Visit 3; 7 months of age): Collection of Safety Information and Blood Sample**

- 1) Collect and review the diary card (DC3) with the parent / guardian, including any AEs, medications, or therapy that occurred since vaccination. If an SAE, including an AESI, has occurred, follow the instructions in [Section 10](#) for reporting it.
- 2) Review temporary contraindications for blood sampling. Ensure the subject has not had any antibiotics within the previous 72 hours (3 days).
- 3) Collect 6 mL of blood (BL2) (see [Section 7](#) for detailed instructions regarding the handling of blood samples).
- 4) Give the parent / guardian a diary card (DC4) to record SAEs and MAAEs from Visit 4 until Visit 5.
- 5) Remind the parent / guardian to expect a telephone call within 14 days before the next visit, Visit 5, and to bring back the diary card when they return for that visit.
- 6) Remind the parent / guardian representative to notify the site in case of an SAE.
- 7) Complete the relevant CRFs for this visit.

##### **5.1.4.2 Vaccination during 2nd Year of Life**

###### **Subgroup 1a**

###### **Telephone Call 4 (within 14 days before Visit 5)**

- 1) Contact the subjects' parent/ guardian by telephone within 14 days before V05 to remind them about the forthcoming study visit.
- 2) If the subject participation in the study is discontinued:
  - a. Review the diary card including any AEs, medications, or therapy that occurred since the last visit.

- b. Ask the subject's parent / guardian if the subject has experienced any SAE in the time since vaccination that has not been reported to the study personnel and / or MAAE. If an SAE, including an AESI, has occurred, follow the instructions in [Section 10](#) for reporting it.
- c. Retrieve the diary card.

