**Visit 5 (12 to 15 months of age): Collection of Safety Information, Blood Sample, and Vaccination**

- 1) Collect and review the diary card (DC4) with the parent/guardian, including any AEs, medications, or therapy that occurred since the last visit. If an SAE, including an AESI, has occurred, follow the instructions in [Section 10](#) for reporting it.
- 2) Perform a physical examination, including, but not limited to, examination of the head (ear, nose, and throat), neck, heart, lungs, abdomen, and extremities. If a routine examination had been performed within the past week by a qualified health care provider, it does not need to be repeated unless there were changes in health status, in which case it may be limited to the affected area
- 3) Measure temperature. If the temperature is  $\geq 38^{\circ}\text{C}$  ( $\geq 100.4^{\circ}\text{F}$ ), postpone vaccination until the condition is resolved.
- 4) Review temporary contraindications for blood sampling. Ensure the subject has not had any antibiotics within the previous 72 hours (3 days).
- 5) Collect 5 mL of blood (BL3) (see [Section 7](#) for detailed instructions regarding the handling of blood samples).
- 6) Review warnings and precautions to vaccinations.
- 7) Review contraindications to subsequent vaccinations and conditions for withdrawal.
- 8) Contact IRT system to receive vaccine assignments.
- 9) Administer the following study vaccines. Each vaccine should be administered in an assigned location (see Operating Guidelines) and documented, appropriately.
  - Meningococcal vaccine (MenACYW conjugate vaccine or MENVEO®): inject IM into the anterolateral area of the thigh, preferably the right thigh.
  - Prevnar 13®: inject IM into the anterolateral area of the thigh, preferably the left thigh (i.e., the opposite leg from that used for meningococcal vaccine administration).
  - M-M-R® II: inject subcutaneously (SC) into the outer aspect of the upper arm
  - VARIVAX®: inject SC into the outer aspect of the upper arm

When multiple vaccines are administered at a single visit, each vaccine should be administered at a different anatomic site. If vaccines are given in the same limb, the injection sites should be separated by 1 inch or more so that any local reactions can be differentiated.

Failure to administer vaccines in the designated limb will not constitute a protocol deviation, but should be recorded as a comment in the CRF.

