### 5.2.11 Follow-up of Discontinuations

The site should complete all scheduled safety follow-ups and contact any subject who has prematurely terminated the trial because of an AE, a protocol deviation, or loss of eligibility, including definitive contraindications.

For subjects where the reason for early termination was lost to follow-up or if the subject withdrew informed consent and specified that they do not want to be contacted again and it is documented in the source document, the site will not attempt to obtain further safety information.

If the subject's status at the end of the study is "Withdrawal by Subject or Parent / Guardian / Legally Acceptable Representative", the site will attempt to contact them for the 6-month follow-up, except if they specified that they do not want to be contacted again and it is documented in the source document.

For subjects where the reason for early termination is voluntary withdrawal, the site will attempt to contact them for the 6-month follow-up except if they specified that they do not want to be contacted again and it is documented in the source document.

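### Telephone Call 4 has no routine SAE/MAAE question, so Visit 4 to Visit 5 safety data, mainly MAAEs, can be incomplete for children lost after that call

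*Protocol*

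**What the plan says.** Protocol 5.1.4.2 sets out TC4 separately for Subgroups 1a, 1b, 2a and 2b, with the same two steps each time. Step 1 is "Contact the subjects' parent/ guardian by telephone within 14 days before V05 to remind them about the forthcoming study visit". Step 2 opens with "If the subject participation in the study is discontinued" and holds everything that concerns safety: diary review (2a), the question about SAEs and MAAEs (2b) and retrieval of the card (2c). Protocol 5.1.3 has the same rule: "If the subject's participation in the study is discontinued, the information recorded on the diary card will be reviewed at this time". The synopsis, the TC4 footnotes to the Tables of Study Procedures, SAP 3.2 and the footnotes to SAP Tables 3.4 to 3.7 repeat it.

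The other calls work differently. For the 8-day calls, 5.1.3 says "Staff will contact the subjects' parent/ guardian by telephone 8 days (+2 days) after each vaccination visit to identify the occurrence of any SAEs", and it names MAAEs as well. The 6-month call asks every family about SAEs and MAAEs.

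The recording tool between Visit 4 and Visit 5 is a card kept at home. The Visit 4 instruction is "Give the parent / guardian a diary card (DC4) to record SAEs and MAAEs from Visit 4 until Visit 5", and the Visit 5 instruction is "Collect and review the diary card (DC4) with the parent/guardian, including any AEs, medications, or therapy that occurred since the last visit". For a child terminated as lost to follow-up, or whose family has withdrawn consent and refused further contact, 5.2.11 says "the site will not attempt to obtain further safety information".

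**The concern.** TC4 is live contact with the family near the end of a long interval that has no other scheduled safety contact. A family that says it will attend is asked nothing about safety. If it then does not attend and cannot be found, DC4 stays at home and no later enquiry is planned. TC4 may have been the last chance to ask.

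SAEs, AESIs and MAAEs are endpoints from Visit 1 to the 6-month contact (Protocol 9.3.2.2). They are reported as the number and percentage of subjects with at least one event (12.1.3). The overall safety set keeps any child with one dose and any safety data (12.2.2.1), and missing safety data are not replaced (12.2.6). A child lost in this way therefore stays in the denominator, and an uncollected event counts as no event.

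**Working it through.** No figure in the plan needs reproducing. The check has two parts: the length of the interval, and the routes by which an event in it can still reach the database.

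**Interval length** (one month taken as 30.4375 days, rounded to whole days)

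- Age at Visit 3: 164 to 224 days (Visit 3 note).
- Age at Visit 4, which is Visit 3 plus 30 to 51 days: 164 + 30 = 194 to 224 + 51 = 275 days.
- Age at Visit 5, Group 1: 12 months to the day before 16 months, or 365 to 486 days.
- Age at Visit 5, Group 2: 12 months to the day before 13 months, or 365 to 395 days.
- Shortest interval, both groups: 365 − 275 = 90 days.
- Longest interval: 486 − 194 = 292 days in Group 1 and 395 − 194 = 201 days in Group 2.

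**Other intervals without a routine safety contact, for comparison**

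- Subgroups 1b and 2b, 8-day call after Visit 5 to Visit 6 (age up to 577 days): at most 577 − (365 + 8) = 204 days.
- Subgroup 2a, Visit 6 to Visit 7: at most 577 − (365 + 30) = 182 days.
- Last visit to the 6-month call: 180 − 51 = 129 to 210 − 30 = 180 days.

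Visit 4 to Visit 5 can be the longest such interval in Group 1. In Subgroup 2b it is about equal to another one (201 against 204 days).

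**Routes for an event between Visit 4 and Visit 5**

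| Situation | SAE (including AESI) | MAAE |
|---|---|---|
| Child attends Visit 5 | DC4, and immediate notification | DC4 |
| Participation discontinued at TC4 | Asked at TC4 | Asked at TC4 |
| Misses Visit 5, reached under 5.2.9 | Health status sought | Health status sought |
| Misses Visit 5, classed as protocol deviation | Safety follow-up under 5.2.11 | Safety follow-up under 5.2.11 |
| Misses Visit 5, voluntary withdrawal | 6-month contact unless refused | 6-month contact unless refused |
| Answers TC4 as continuing, misses Visit 5, then unreachable or refuses contact | Immediate notification by the parent only | No scheduled route |

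Only the last row is open. It is narrower than all children who miss Visit 5, and it bears mainly on MAAEs, because the request to notify the site at once (5.1.3 and Visit 4) covers SAEs only.

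**The case against.** The strongest reply is that collection is layered and TC4 is only one layer.

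- A missed Visit 5 does not make a child lost to follow-up. Section 5.2.9 requires documented calls and certified mail. Section 5.2.10 reserves the lost class for families who cannot be found, with the letter returned unsigned. A parent who signs for the letter but gives no news and does not come is classed as a protocol deviation, and that child gets the scheduled safety follow-ups.
- The discontinuation condition can be read to cover a parent who says on the call that the child is stopping, since the card is reviewed at that time.
- In Group 1 a missed appointment can be rebooked within a window of about four months.
- Safety is observational and SAP 5.1.4 tests no hypothesis, so no decision rule depends on this.

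All of this stands, and it limits the size of the gap. It does not close it: a family that says it will come is not asked, on either reading of the condition, and 5.2.9 yields data only if the family is reached.

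A reader might infer that safety data for this interval go unrecorded for every child who misses Visit 5, or that this is the longest unasked interval in every subgroup. The table and the Subgroup 2b figures above show otherwise. A reader might also see a bias between groups, because the interval can be 292 − 201 = 91 days longer in Group 1. That difference comes from the Visit 5 age windows, and a question at TC4 would not remove it.

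**Conclusion.** The point holds in a limited form. TC4 is the only scheduled call without a routine SAE/MAAE question. Children whose family answers it, who then miss Visit 5 and become unreachable, can have incomplete Visit 4 to Visit 5 data, mainly MAAEs. Whole-study rates in the overall safety set can be slightly low as a result.

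The number of such children cannot be derived from the documents. The 34.1% non-evaluable allowance (2628 − 1732 = 896 children) covers every reason for exclusion from the per-protocol set and does not measure this loss. A reader might assume that 5 to 15% miss Visit 5 (131 to 394 of 2628) with a 2 to 4% SAE risk over the interval, and conclude that about 3 to 16 children have a missed SAE. Neither rate is in the documents. The product also counts all no-shows, including those who never answered TC4 or were later recovered, and assumes that no parent reports an SAE unprompted. It is at most a ceiling under those assumptions.

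The judgement that the true number is small rests on the narrowness of the open route, not on a stated rate. Sample size, power and alpha are unaffected.

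**What to change.** In Telephone Call 4 for all four subgroups, make step 2b unconditional: ask every family about SAEs (including AESIs) and MAAEs since Visit 4, record the answers, and report SAEs under Section 10. Keep diary review and card retrieval at the call for discontinued children only. Align the synopsis, Protocol 5.1.3, the TC4 footnotes and the matching SAP text.

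The cost is a few minutes on a call that already takes place, and reconciliation of events noted at TC4 with DC4 at Visit 5. The change does not help families who do not answer TC4, or events after the call. Priority: minor.
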